## **13.2. Reporting of Adverse Events**

Information regarding AEs is to be obtained by questioning or examining the subject.

For subjects who participated in Study ATB200-03, AEs will be recorded in the eCRF and subject's source record beginning after the first dose of open-label study drug until 30 days after the last treatment visit.

A single diagnosis should be entered when known. If a clear diagnosis cannot be determined at the time of the eCRF and subject's source record entries, each sign and symptom must be recorded individually, until a final diagnosis is established. Pompe-related conditions, signs,

symptoms, etc, that are present in the subject's medical history should only be reported as AEs if they worsen (ie, increase in severity) during the subject's participation in the study.

For each AE reported, the date and time the event started and ended, action taken, outcome (resolved, resolved with sequelae, ongoing, or fatal), and severity must be noted.

All subjects who have AEs, whether or not considered associated with the use of study drug, must be monitored to determine the outcome. The clinical course of the AE will be followed up according to accepted standards of medical practice, even after the end of the period of observation, until a satisfactory explanation is found or the investigator considers it medically justifiable to terminate follow-up. Should the AE result in death, a full pathologist's report should be supplied, if possible. For all AEs that require or result in subject discontinuation from the study, relevant clinical assessments and laboratory tests will be repeated as clinically appropriate, until final resolution or stabilization of the event(s).

If the investigator considers it necessary to report a nonserious AE in a study subject more than 30 days after the last visit, he or she should contact Amicus to determine how the AE should be documented and reported.

### **13.3. Reporting Requirements for Serious Adverse Events**

If an AE is serious (as defined in Section 13.1.2), the investigator must submit an SAE report form at the time the SAE is identified. All SAEs must be immediately reported by the investigator to Amicus or Amicus' designee, but no later than 24 hours after any study site personnel is aware of the event. Serious adverse event report forms must be faxed to the designated safety fax number ([contact]) or sent via email to [contact]. All supporting documentation available at the time of reporting, with all subject identifiers redacted in accordance with local requirements, must be included in the fax along with the SAE report form.

The initial report must be completed as soon as possible. All known details of the SAE and an assessment of the causal relationship between the event and study drug, or study procedure should be included in the initial report. All information not available at the time of the initial report (eg, event end date, discharge summary, or results of diagnostic procedures/evaluations related to the event) must be provided in a follow-up report. Follow-up information must be reported using the designated fax number within 24 hours of receipt at study sites.

Every attempt should be made to describe events in terms of a diagnosis. If a clear diagnosis has been made, individual signs and symptoms should not be recorded unless they represent atypical or extreme manifestations of the diagnosis, in which case they should be reported as separate events. If a clear diagnosis cannot be established, each sign and symptom must be recorded individually.

Study endpoints that meet SAE criteria (as per Section 13.1.2) must also be immediately reported by the investigator to Amicus or Amicus' representative but no later than 24 hours after any study site personnel is aware of the event.

If a nonserious event becomes serious, the event must be reported as described above.

If the investigator becomes aware of an SAE in a subject or receives an unsolicited report of an SAE from a subject more than 30 days after the last treatment, and considers the event possibly, probably, or definitely related to previous study treatment, he or she should contact the Amicus medical monitor to determine how the SAE should be documented and reported.

The Amicus Safety Physician will determine the expectedness of AEs according to current safety reference document (eg, current Investigator's Brochure or other safety-related information as available).

### **13.3.1. Additional Reporting Requirements for Suspected Unexpected Serious Adverse Reaction**

Any AE that is serious, unexpected, and associated with the use of the study drug (suspected unexpected serious adverse reaction [SUSAR], also referred to as Expedited Safety Report and Investigational New Drug Safety Report) has additional reporting requirements. All investigators conducting clinical studies with the study drug will be notified of such events and must inform their IRBs/IECs/REBs as required in accordance with local law. Amicus will ensure that SUSARs are reported to regulatory agencies in accordance with local law in each country where study sites are located.

- If the SUSAR is fatal or life-threatening, associated with the use of the study drug, and unexpected, regulatory authorities and IRBs/IECs/REBs will be notified within 7 calendar days after Amicus learns of the event.
- If the SUSAR is not fatal or life-threatening but is otherwise serious, associated with the use of the study drug, and unexpected, regulatory authorities and IRBs/IECs/REBs will be notified within 15 calendar days after Amicus learns of the event.

Safety updates will be provided periodically to the regulatory authorities and IRBs/IECs/REBs responsible for the study according to the rules in effect in each country where study sites are located. These updates will include information on SUSARs and other relevant safety findings.

### **13.3.2. Overdose/Underdose**

A product overdose/underdose (whether accidental or intentional) is considered by Amicus to be an AE and must be recorded as such in EDC. If a subject experiences an overdose or an underdose during the course of the study (as defined below for each product, whether symptomatic or not), the Amicus medical monitor must be notified within 5 working days of the investigator or study personnel first becoming aware of the overdose/underdose.

- Overdose
  - cipaglucosidase alfa:  $\geq 20\%$  higher than the assigned dose of study drug for a single administration ( $20 \text{ mg/kg} \times \text{patient weight}$ )
  - miglustat:  $\geq 1$  capsule more than the assigned dose of study drug for a single administration

- Underdose
  - cipaglucosidase alfa:  $\geq 20\%$  lower than the assigned dose of study drug for a single administration ( $20 \text{ mg/kg} \times \text{patient weight}$ )
  - miglustat:  $\geq 1$  capsule less than the assigned dose of study drug for a single administration (eg, if a subject is supposed to receive 4 capsules, but only receives 1, 2, or 3 capsules; or if a subject is supposed to receive 3 capsules but only receives 1 or 2 capsules)

Follow-up information must be forwarded on the outcome of the overdose/underdose as applicable. If an SAE occurs in conjunction with the overdose/underdose, the same SAE reporting requirements described in Section 13.3 apply.

#### **13.3.3. Missed Dose**

If a subject is unable to schedule a treatment (infusion) up to 7 days after the scheduled date, this is considered as a missed dose. The subject will receive his or her next dose per his or her schedule, ie, approximately 4 weeks following the previous dose, since the subject missed a dose at 2 weeks following the last dose. This is recorded as a protocol deviation. Any AE that occurs as a result of missed dose should be recorded as such. The Amicus medical monitor should be notified as soon as feasible after the investigator or study personnel first become aware of the missed dose. Follow-up information on the outcome must be forwarded as applicable. If an SAE occurs in conjunction with the missed dose, the same SAE reporting requirements described in Section 13.3 apply.

Study subjects who missed infusions close to their scheduled assessments at Week 12, Week 26, or at any of the study visits scheduled every 26 weeks after Week 26 should postpone the assessments and receive a sufficient number of catch-up infusions prior to undergoing the study assessments. Each instance of missed infusion should be discussed with, and course of action approved by, the medical monitor. A reason for the missed visit should be entered into the EDC. The relevant IRBs, IECs, and REBs should be notified of any deviations from the protocol.

#### **13.4. Reporting of Pregnancy**

Pregnancy information for female subjects and female partners of male subjects participating in the study is collected by Amicus. Pregnancy, in and of itself, is not regarded as an AE (unless there is a suspicion that study drug may have interfered with the effectiveness of a contraceptive medication).

If a female subject becomes pregnant during the course of this study, or if the female partner of a male subject becomes pregnant during the subject's participation in the study, the event must be reported within 5 working days of the investigator or study personnel becoming aware of the pregnancy. Study drug will be discontinued, and the subject will be monitored for the duration of pregnancy and the baby for 6 months following birth. If an SAE occurs in conjunction with the pregnancy, the SAE must be reported as described in Section 13.3. Amicus will provide pregnancy report forms and instructions to study personnel regarding collection of pregnancy and outcome information (subject to receipt of data privacy release approvals where required under local privacy laws).

The outcome of all pregnancies (spontaneous miscarriage, elective termination, normal birth, or congenital abnormality) must be followed up and documented even if the subject was withdrawn from the study.

All reports of congenital abnormalities/birth defects are SAEs. Spontaneous miscarriages should also be reported and handled as SAEs. Elective abortions without complications should not be handled as AEs.

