## **8.4. Definition of the End of Study**

End of study is defined as the date of the last subject's last visit. The final analysis will be performed for the final CSR based on a data cutoff date of 31 December 2024. Any data collected after this date will be provided as an addendum to the final CSR when all subjects have completed the study or have been withdrawn from the study. Upon approval of this amendment, subjects who remain in the study will follow the Schedule of Assessments in [Appendix 1](#) ([Table 10](#)).

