##### **9.2.1.1. Inclusion Criteria**

1. Subject must provide signed informed consent prior to any study-related procedures being performed. If the subject is under 20 years of age, the subject must provide written informed consent. In Japan, the subject's parental guardian (or legal representative) must also sign the informed consent form.
2. Subjects must have completed Study ATB200-03.

Note: Subjects who were forced to withdraw from Study ATB200-03 for a logistical reason not related to the efficacy or safety of cipaglucosidase alfa/miglustat (eg, hospitalization for a car accident, COVID-19 pandemic, or emergency surgery) and which resulted in several consecutive missed doses may be eligible to participate in this study upon approval by the Amicus medical monitor.

3. Female subjects of childbearing potential and male subjects must agree to use medically accepted methods of contraception during the study and for 90 days after the last dose of study drug.

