### **9.4. Subjects of Reproductive Potential**

Subjects must be willing to apply highly effective contraception during the study and through the duration as defined below and for 90 days after the final dose of study treatment.

The allowed methods of contraception described in the following text are only effective when used consistently, correctly, and in accordance with the product label. For Japanese subjects, only approved contraceptive measures in Japan are considered as effective measures. The investigator is responsible for ensuring subjects understand how to properly use these methods of contraception. A highly effective birth control is defined as one that results in a low failure rate (ie, < 1% per year) when used consistently and correctly.

Women of child-bearing potential are defined as all women physiologically capable of becoming pregnant, ie, fertile, following menarche and until becoming post-menopausal unless permanently sterile. Highly effective methods of contraception include the following:

- combined (estrogen- and progestogen-containing) hormonal contraception associated with inhibition of ovulation: oral, intravaginal\*, transdermal\*
- progestogen-only hormonal contraception associated with inhibition of ovulation: oral, injectable\*, implantable\*
- intrauterine device
- intrauterine hormone-releasing system
- bilateral tubal occlusion
- vasectomized partner
- sexual abstinence

Note: \* Indicates products not approved in Japan.

Note: Periodic abstinence (eg, calendar, ovulation, symptothermal, and post-ovulation methods) and withdrawal are not acceptable methods of contraception.

Note: Women are considered post-menopausal and not of child-bearing potential if they have had 12 months of natural (spontaneous) amenorrhea with an appropriate clinical profile (eg, age appropriate, history of vasomotor symptoms) or 6 months of spontaneous amenorrhea with a serum FSH level  $> 40$  mIU/mL and estradiol  $< 20$  pg/mL, or have had surgical bilateral oophorectomy, only when the reproductive status of the woman has been confirmed by follow-up hormone level assessment and she is considered not of child-bearing potential.

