A man is considered fertile after puberty unless permanently sterile by bilateral orchidectomy. Male subjects and their partners must use highly effective methods of contraception (ie, condom in male subjects and highly effective contraception, as listed previously in this section, in their female partners) for the entire duration of the study and continue to use contraception and refrain from fathering a child for 90 days following the study treatment.

In the event of pregnancy in a female subject, study drug must be discontinued. Pregnancies occurring during study participation (female subject or a female partner of a male subject) must be reported to Amicus and followed as described in Section [13.4](#).

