### 12.3.11.2. Pregnancy Tests

All female subjects of childbearing potential will have a urine pregnancy test performed at infusion visits. If the urine pregnancy test has a positive result, study drug will not be administered and a confirmatory serum pregnancy test will be performed. Any pregnancy that occurs during the study period must be reported, and that subject must be withdrawn from the study (see Section 13.4).

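### Contraception is required for 90 days after the last dose, but the duty to report a partner pregnancy is tied to an undefined study participation that may end sooner

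*Protocol*

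**What the plan says.** **Precaution period.** Protocol 9.2.1.1 sets one condition for men and for women who could become pregnant. They "must agree to use medically accepted methods of contraception during the study and for 90 days after the last dose of study drug". Section 9.4 repeats the period ("for 90 days after the final dose of study treatment") and adds that men must "continue to use contraception and refrain from fathering a child for 90 days following the study treatment".

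**Reporting duty for partners.** Section 13.4 states that "if the female partner of a male subject becomes pregnant during the subject's participation in the study, the event must be reported". Section 9.4 has a similar limit: "Pregnancies occurring during study participation (female subject or a female partner of a male subject) must be reported to Amicus".

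**Reporting duty for female subjects.** Three phrases are used. Section 13.4 begins "If a female subject becomes pregnant during the course of this study, or if the female partner of a male subject becomes pregnant". Section 9.4 refers to study participation, as just quoted. Section 12.3.11.2 says "Any pregnancy that occurs during the study period must be reported, and that subject must be withdrawn from the study". None of these periods is defined for pregnancy reporting. The nearest definition is in Section 8.4: "End of study is defined as the date of the last subject's last visit".

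**Last scheduled contact.** Tables 4 and 10 place the follow-up visit at least 30 days after the last dose, with a ±3-day window. Section 12.2.6 calls it a 30-day safety follow-up, and SAP 3.1 counts a 30-day follow-up as part of the study. Sections 9.3 and 12.3.12 provide later testing, at 6 and 12 months, for antibody-positive subjects only. For subjects continuing under Amendment 3, Appendix 1 refers back to Sections 9 and 13 without change.

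**The concern.** The 90 days are the protocol's own statement of how long conception should be avoided after exposure. One would expect a conception inside that period to be reported, since it is the event that the precaution is meant to prevent. For partners of male subjects, the duty instead follows the man's participation. That could end well before day 90.

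The case is not purely theoretical. Section 9.3 lists planning to conceive, for men as well as women, as a reason for withdrawal. A man who leaves for that reason may be more likely than others to have a partner conceive before day 90, and the reporting duty may by then have lapsed.

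What is at stake is completeness of the pregnancy record in a study whose primary objective is long-term safety. No statistical result is at stake. Pregnancy is not among the safety endpoints in Protocol 15.1.1 or SAP 2.3.1, and SAP 7.3 puts urine pregnancy test results in a listing only.

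**Working it through.** The plan gives no figure for this gap, so the check compares the time windows.

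**Inputs**
- Precaution period: 90 days after the last dose (9.2.1.1, 9.4).
- Partner reporting: until the man's participation ends (13.4, 9.4). Call that day E, counted from the last dose. The protocol does not give E.
- Assumption: E is the day of the follow-up visit. The visit is at least 30 days after the last dose, ±3 days (Tables 4 and 10), with no upper limit beyond that window.
- Antibody-positive subjects: testing at 6 and 12 months after the last dose (9.3, 12.3.12).

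**Formula for partners:** days of the 90 without a stated duty = max(0, 90 − E).

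| Participation ends (E) | Days without a stated duty | Share of 90 days |
|---|---|---|
| Day 30 | 90 − 30 = 60 | 60/90 = 67% |
| Day 33 | 90 − 33 = 57 | 57/90 = 63% |
| Day 60 | 90 − 60 = 30 | 30/90 = 33% |
| Day 90 or later | 0 | 0% |
| About day 180 (6-month antibody test counted as participation) | 0 | 0% |

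**Which pregnancies fall in the gap.** Only conceptions after participation ends. If a pregnancy began during participation and came to light later, it is still reportable, because the 5 working days in 13.4 run from the site's awareness.

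**Whether another rule closes the gap**
- The sentence in 13.4 on following every pregnancy to its outcome, even after withdrawal, governs a pregnancy already known. It sets no window for the first report.
- The late SAE route (13.1.2, 13.3) needs a serious event in a subject, or reported by a subject, that the investigator considers related.
- The late nonserious AE route (13.2) concerns events in a study subject and depends on the investigator's view that a report is needed.
- Under 13.4 a pregnancy is not itself an AE unless interference with a contraceptive medication is suspected.

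None of these requires an uncomplicated late partner pregnancy to be reported.

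**Female subjects.** Take the course of the study to run to the last subject's last visit (13.4 read with 8.4). A woman who leaves early is then covered for as long as others remain, so the gap is 0 days while they do. The study-participation phrase in 9.4 could be read more narrowly. The study-period phrase in 12.3.11.2 settles neither reading. The result is inconsistent wording, not a demonstrated gap.

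**With a 90-day trigger for everyone,** the uncovered period is 90 − 90 = 0 days under every reading.

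**The case against.** The strongest reply is that the size rests on a term the protocol leaves open. The follow-up visit has a minimum day and no clear maximum, so the result could lie anywhere from about 60 days to 0. This stands: two thirds of the period is the upper end under one assumption and should not be read as an established figure.

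A reader might infer that the few late pregnancies on record would lean towards bad outcomes, because miscarriages and birth defects are SAEs under 13.4 while normal pregnancies go unreported. The documents do not support this for partners. The late routes in 13.1.2, 13.2 and 13.3 are written for events in, or reported by, a subject, and a partner is not a subject. It is unclear whether a late partner case would enter by those routes at all.

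A reader might also infer that female subjects have the same gap. Section 13.4 read with 8.4 gives a reasonable reading under which they do not.

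Other points on that side have partial force:
- The affected group is narrow: essentially men who stop the drug altogether and whose partner conceives despite the required contraception. For subjects who move to commercial or post-trial drug, the documents do not say how the 90 days apply.
- The sponsor's pregnancy forms and instructions, mentioned in 13.4, are not in the documents and may state a window. If so, the protocol should carry it too.
- No document says that the reporting window must equal the contraception window. That is true, but the protocol offers no reason for reporting to stop sooner, and a site following its text would have no duty to report.

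**Conclusion.** The point holds as a small safety-reporting gap for partners of male subjects. The precaution period runs to day 90, while the reporting duty stops with an undefined participation, and no other provision extends it. If participation ends at the follow-up visit, up to about 60 of the 90 days have no stated duty. That falls to 0 if the visit is on day 90 or later, or if antibody follow-up counts as participation. For female subjects, the finding is only that three phrases should be aligned.

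The number of subjects affected is not given. With at most about 110 subjects in the study (Section 9.1), it is likely to be few. No endpoint, analysis population or planned summary changes. This is an inexpensive improvement that the sponsor could make; it does not threaten the study's conclusions. Confidence is medium, because the result depends on how participation is read and on sponsor instructions that cannot be seen.

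**What to change.** In Sections 9.4 and 13.4, use one trigger: any pregnancy in a subject or a subject's partner conceived up to 90 days after the last dose of study drug is to be reported and followed to outcome, whether or not the subject has left the study. Put matching wording in 12.3.11.2 for female subjects. Appendix 1 needs no separate change, since it refers back to Sections 9 and 13 and, through its own Section 12.1, to Section 12.3.

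At the existing follow-up visit in Tables 4 and 10, remind subjects of this duty. The reminder is the useful part: a question asked at about day 30 cannot detect a conception that happens later.

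The cost is protocol wording and a short reminder at a visit already planned, plus a few extra reports to follow up. Conceptions after the last contact would still rely on self-report, so the change closes the gap in the duty without guaranteeing that every case is captured.
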